Subjects will be screened for enrollment in this study against the inclusion and exclusion criteria according to the standard procedures of the investigational site.

Following recruitment, a subject will be considered enrolled (the point of enrollment) once he/she signs and dates the informed consent form (ICF). Safety events and device issues will, however, only be reported during the period of exposure to the investigational PET/MR device (from the time the subject enters until the time the subject leaves the PET/MR suite), and not for clinically indicated imaging (e.g. PET/MR or PET/CT) procedures that may be observed after the patient provides consent but are not a consequence of study participation.

Once enrolled, the subject will be assigned a unique subject number, which will not contain information that could identify the subject. The unique subject number will be used to label case report form (CRF) data for the subject throughout his/her participation in the study.

■ Criteria for Withdrawal/Discontinuation

A subject may withdraw from study participation at any time, for any reason. The investigator may withdraw a subject at any time, for any reason. The reasons for withdrawal and discontinuation for any subject shall be recorded. These will be reported to the Sponsor. The EC should be notified per their notification of subject withdrawal policy.

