In the event of a medical emergency, the scan will be stopped immediately and facility's emergency response plan will be followed. The subject will be provided with emergency care as needed.

The subject's care shall take precedence over any imaging associated with the study. In the event the subject experiences discomfort or wishes to stop the exam for any reason, the exam will be immediately stopped and appropriate follow up response will occur. The event will be recorded in compliance with US FDA and GE Healthcare safety reporting requirements.

Incidental Findings

The additional PET/MR procedures performed in this study are for research only and are not intended for diagnostic use. Should the device operator observe what they interpret to be a potential abnormality, the investigator will evaluate the findings and alert the patient if necessary. The investigator may recommend diagnostic exams to be performed independent of the study. No medical or diagnostic care of any kind will be rendered based on study image sets using the research PET/MR.

Activities after PET/MR Scanning

Upon completion of the exam, the device operator or those assisting him/her will assist the subject from the device and out of the scan area. Any reported safety or device issues will be recorded to the CRF up until the time the subject leaves the PET/MR suite.

After the exam is complete and the subject has left the PET/MR suite, the device operator will complete the CRF and store the image sets for the scan, which will be labeled with the subject's unique ID number. All images collected from clinical sites will be sent to the Sponsor or its delegate for investigational post-processing with the investigational technology prior to image reads.

Follow-up Visits

All patient procedures will be conducted during a single visit. No follow-up visits are required.

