8. SAFETY

■ Anticipated Adverse Events

MR technologies up to 3.0T have been used in clinical applications for over 30 years and have a well-documented safety profile. Similarly, PET scanners are widely used in clinical practice. The PET/MR scanner does not involve any risks other than those normally associated with routine clinical PET and MRI scans, similar to those already performed in many hospitals. The following are some discomfort one may experience during a PET/MR scan session.

Movement of metal objects: PET/MR systems operate in a high field magnetic field typical of MRI systems, which can cause movement or projectile motion of certain ferrous metal objects. Though injuries are rare (occurring in less than one of 100,000 patients), small objects can cause bruises or cuts, and large objects can cause severe trauma or even death.

Implants: Objects embedded within the body can be affected by the strong external magnetic field near and inside of the PET/MR device during an MRI exam, causing movement and/or electronic malfunction that can lead to injury or even death.

Warming and burns: Radiofrequency (RF) energy transmitted by the PET/MR system during MRI scanning can result in generalized or localized heating of body tissues, occurring in about 5-10% of

patients. Some subjects may experience sensations of warming and/or perspiration, which can be uncomfortable. Though warming can cause burns, severe injuries are rare.

Peripheral nerve stimulation (PNS): During a PET/MR exam, rapidly changing magnetic fields during MRI exams can cause stimulation of nerves, causing unusual generalized or localized “tingling” sensations, known as peripheral nerve stimulation (PNS). PNS normally occurs in 5-10% of subjects, but may occur in up to 50% of subjects under certain conditions.

Acoustic Noise: During PET/MR, the MRI system is capable of generating acoustic noise levels higher than 99dB. The acoustic noise levels of the system do not exceed 140 dB under worst-case conditions. Sometimes, transient hearing loss or “ringing” in the ears (tinnitus) can occur, which it typically is mild and resolves spontaneously after scanning. Severe or chronic hearing conditions can occur if proper hearing protection is not used, but are rare (occurring in less than one of in 100,000 patients).

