There is always a chance of unexpected risks. Throughout the study, the Sponsor will evaluate and update safety information in study documents.

■ Adverse Event Definitions

Adverse Event (AE): any untoward medical occurrence, unintended disease or injury, or untoward clinical signs (including abnormal laboratory findings) in subjects, users or other persons, whether or not related to the investigational medical device [ISO 14155:2011 3.2]. This includes events related to the investigational device or the comparator and to the procedures involved. For users or other persons, this is restricted to events related to the investigational medical device.

Serious Adverse Event (SAE): an adverse event that led to death; led to a serious deterioration in the health of the subject, that either resulted in a life-threatening illness or injury, a permanent impairment of a body structure or a body function, or in-patient or prolonged hospitalization, or medical or surgical intervention to prevent life-threatening illness or injury or permanent impairment to body structure or a body function; or led to fetal distress, fetal death or a congenital abnormality or birth defect. Planned hospitalization for a pre-existing condition, or a procedure required by the protocol without serious deterioration in health, is not considered a SAE [ISO 14155:2011 3.37].

Adverse Device Effect (ADE): an adverse event related to the use of an investigational medical device [ISO 14155:2011 3.1]. This includes any adverse events resulting from insufficient or inadequate instructions for use, deployment, implantation, installation, or operation, or any malfunction of the investigational medical device. This includes any event that is a result of a user error or intentional misuse of the investigational device [ISO 14155:2011 3.43].

Serious Adverse Device Effect (SADE): an adverse device effect that has resulted in any of the consequences characteristic of a serious adverse event [ISO 14155:2011 3.36].

Device deficiency: an inadequacy of a medical device with respect to its identity, quality, durability, reliability, safety, or performance, such as malfunctions, use errors, and inadequate labelling [ISO 14155:2011 3.15].

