Unanticipated serious adverse device effect (USADE): a serious adverse device effect, which by its nature, incidence, severity, or outcome has not been identified in the current version of the risk analysis report [ISO 14155:2011 3.42]. In the United States, any serious adverse effect on health or safety or any life-threatening problem or death caused by, or associated with, a device, if that effect, problem, or death was not previously identified in nature, severity, or degree of incidence in the study documents, will be reported in accordance with 21 CFR §812.3 and applicable laws and regulations.

■ Documentation of Safety Events

All adverse events (AE), including all serious adverse events (SAE), are required to be collected, investigated, and documented during the study reporting period, as defined in the study procedure as the time the subject enters until the time the subject leaves the PET/MR suite. Documentation will include:

- Description of Event

- Date of onset and resolution
- Severity (mild, moderate, or severe)
 - *Mild*: Symptom(s) barely noticeable to the subject or does not make the subject uncomfortable. The AE does not influence performance or functioning. Prescription drugs are not ordinarily needed for relief of symptom(s).
 - *Moderate*: Symptom(s) of a sufficient severity to make the subject uncomfortable. Performance of daily activities is influenced. Treatment of symptom(s) may be needed.
 - *Severe*: Symptom(s) of a sufficient severity to cause the subject severe discomfort. Treatment for symptom(s) may be given.
- Serious (yes/no)
- Causal relationship to investigational medical device? (not related, possibly related, or related)
 - *Not related*: The adverse event is reasonably expected to be related to (or caused by) a concurrent illness, effect of another device/drug or other cause, and is unlikely related to the investigational product.
 - *Possibly related*: The adverse event is reasonably expected to be related to the investigational product, and an alternative etiology is equally or less likely compared to the potential relationship to investigational product.
 - *Related*: There is a strong relationship to investigational product or recurs on re-challenge, and another etiology is unlikely or there is no other reasonable medical explanation for the event.
- Treatment given and/or action taken (procedure stopped, withdrawn from study, or no action)

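### Safety recording stops when the subject leaves the PET/MR suite, so effects of the research scan first reported later are left out of the safety endpoint, and events still open at exit have no stated route to a resolution date or to reclassification as serious.

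*Combined protocol and SAP*

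**What the plan says.** Three places close the recording window at the same moment.

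- Section 4, Recruiting and Screening: safety events and device issues are reported only for the period of exposure, "from the time the subject enters until the time the subject leaves the PET/MR suite". Events of clinically indicated imaging that do not result from taking part in the study are excluded.
- Section 5, Activities after PET/MR Scanning: "Any reported safety or device issues will be recorded to the CRF up until the time the subject leaves the PET/MR suite".
- Section 8, Documentation of Safety Events: all AEs, serious ones included, are collected in the reporting period "as defined in the study procedure as the time the subject enters until the time the subject leaves the PET/MR suite".

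The exam lasts up to 1 hour with about 30 minutes of scanning, and under Follow-up Visits, "No follow-up visits are required".

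Other provisions look beyond that window. The fields required for each AE include "Date of onset and resolution". Under Anticipated Adverse Events, transient hearing loss or tinnitus "typically is mild and resolves spontaneously after scanning". The SAE definition includes "a permanent impairment of a body structure or a body function, or in-patient or prolonged hospitalization". The adverse device effect definition covers any AE related to use of the device and sets no time limit. Section 6 (Safety Assessments) speaks of any AE or SAE during the study, which is wider than time in the suite.

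The safety endpoint (Section 3) is the type and number of AEs, SAEs and device issues. It is summarised descriptively in Section 10.

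**The concern.** The apparent purpose of the narrow window is to keep out events caused by the subject's clinical PET/CT or PET/MR. As written it does more than that, because it also excludes an event caused by the research scan if the subject first mentions it after leaving. Skin injury from heating and a hearing change are the obvious candidates among the effects that the protocol lists.

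A second, smaller gap concerns events that begin in the suite and are still present at exit. A resolution date is required, but nothing says how it is to be obtained. Some SAE criteria, such as hospitalisation or permanent impairment, may become known only later, and nothing says how an event already recorded is then upgraded.

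The results are intended for a 510(k) submission. A reader of the safety tables could take them as the full yield of device effects, when they describe only what was seen or reported in the suite.

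**Working it through.** The plan states no figure on this point, so there is nothing to reproduce. The check is a comparison of provisions by type of event, followed by a test of whether the loss can be sized.

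**Provisions by type of event**

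| Event | In the Section 8 reporting period? | Counted? | What is left open |
|---|---|---|---|
| Starts and resolves in the suite | Yes | Yes | Nothing |
| Starts in the suite, open at exit | Yes | Yes | Source of the resolution date; later change to SAE |
| Non-serious, related to the research scan, first reported after exit | No | No | The event itself |
| Serious, related to the research scan, first reported after exit | No | No rule admits it to the tables | Expedited reporting may still apply |
| Due to clinically indicated imaging | Excluded by Section 4 | No | Nothing; this is intended |

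For the fourth row, Section 8 (Reporting of Safety Events) asks for SAEs and unanticipated serious device effects within 72 hours and study-related deaths within 24 hours. It also lets the sponsor request further information. These are reporting duties for serious events. They do not extend the reporting period, do not cover non-serious AEs, and do not say that a later event enters the tables.

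For the second row, Section 10 (Handling of Missing Data) uses collected data without imputation, so a resolution date that is not obtained stays missing.

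**Can the loss be sized?**

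Inputs: n = 75 (maximum enrolment); p = 5 to 10% for warming and, normally, 5 to 10% for peripheral nerve stimulation (Section 8, Anticipated Adverse Events).

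- Expected subjects with each effect = n × p: 75 × 0.05 = 3.75 and 75 × 0.10 = 7.5.
- Expected lost events = n × p × f, where f is the share first reported after exit. The documents give no f.
- With assumed f of 0, 25, 50 and 75%, the product is 0, 0.94, 1.88 and 2.81 at p = 5%, and 0, 1.88, 3.75 and 5.63 at p = 10%. The result depends entirely on f.
- Warming and nerve stimulation are also the wrong p. The protocol ties both to the scan itself, so they are the effects that an in-suite window is best placed to catch. For the effects more likely to surface later, it calls severe injury from warming rare and gives no rate for transient tinnitus.

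The loss therefore cannot be estimated.

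**What a zero would mean**

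If no event of a given type is recorded among n scanned subjects, the one-sided 95% upper bound is 1 − 0.05^(1/n). This is 3.9% for n = 75 and 4.9% for n = 60. Under the present window the bound applies only to events recorded before suite exit.

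**The case against.** The best defence is that the window is deliberate, disclosed and consistent. Subjects carry a clinical radiotracer and some may have had contrast, so later events are hard to attribute. The study gives no drug, is classed as not significant risk, requires no clinical follow-up and tests no hypothesis. This supports having no scheduled follow-up. It does not support discarding an event that the site already knows of and judges related to the research scan, since the causality categories in Section 8 exist to make that separation.

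A second defence is that documentation can continue after exit. The operator completes the CRF once the subject has left. An exam stopped for discomfort gets an appropriate follow-up response. Section 11 has CRFs completed as information arrives and allows clarification forms and later corrections. This stands in part: there is room to complete an open event, but no rule that it be done. The CRF is not among the documents, so it cannot be said to lack an *ongoing* option.

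Two stronger readings are tempting, and the documents support neither.

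- A reader might infer that ongoing events go uncounted. They do not: an AE that starts in the suite falls inside the reporting period whether or not it has resolved.
- A reader might infer that the window forces SAE counts towards zero. Life-threatening injury, or intervention to prevent impairment, can be evident in the suite. Serious events may be rare anyway: the protocol puts metal-object injury and severe or chronic hearing conditions each below 1 in 100,000, or under 75/100,000 = 0.00075 expected in 75 subjects.

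**Conclusion.** The point holds in a limited form. Effects of the research scan first reported after suite exit are left out of the type-and-number endpoint by the stated window. Events open at exit are counted, but they have no stated route to the resolution date or to SAE reclassification. The expedited-reporting provisions soften this for serious events without closing it.

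The size is unknown. It would be wrong to read the 3.75 to 7.5 expected warming or nerve stimulation events as events lost. The practical weight is moderate, because safety is descriptive and the risk class is low. The change is still worth making, because the tables support a regulatory submission and the remedy is cheap.

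The conclusion assumes that no rule in the CRF or in the separate SAP, neither of which is available here, already covers these events.

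**What to change.** Keep the single visit and reconcile Section 4 (Recruiting and Screening), Section 5 (Activities after PET/MR Scanning), Section 6 (Safety Assessments) and Section 8 (Documentation and Reporting of Safety Events) as follows.

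1. An AE open at exit is recorded as ongoing. Its outcome and SAE status are updated from site records up to a fixed cut-off, such as database lock.
2. An event spontaneously reported to the site after exit, and judged possibly related or related to the research scan, is recorded. The exclusion of events due to clinically indicated imaging stays.
3. In-suite events and later spontaneously reported events are tabulated separately, and the in-suite table is labelled *events observed in the suite*.

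The cost is wording and occasional extra CRF entries, with no added contact, visit or test. The downsides are slightly higher AE counts, passive and therefore incomplete ascertainment of later events (which is why they need their own table), and possible ethics committee approval if the amendment is judged substantial.

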6. STUDY DATA COLLECTION AND ASSESSMENTS

Primary Assessment

Independent Reader Determination of Diagnostic Image Quality

Diagnostic image quality will be rated on a 5-pt Likert scale by at least 2 independent board certified nuclear medicine physician and/or radiologists for all evaluable image sets (including all clinically acquired MR image sets able to be successfully post-processed that are complete image sets [not from cases of withdrawal or critical deviation that could impair to the quality of data]). Independent reads will be conducted outside of the clinical care environment according to the procedures specified in the Blinded Image Evaluation (BIE) plan prepared by the Sponsor prior to the start of image reading. Identifiable subject information will be removed prior to independent reads.

Diagnostic image quality will be recorded on a 5-pt Likert scale, where ratings of ≥ 3 are considered acceptable for diagnostic use and ratings of 1-2 are considered unacceptable for diagnostic use, as follows:

1. **Unacceptable** (cannot be used for diagnostic use)
2. **Poor** (not completely suitable for diagnostic use)
3. **Acceptable** (suitable for diagnostic use but with minor defects)
4. **Good** (good suitability for diagnostic use)
5. **Excellent** (excellent suitability for diagnostic use)

The reader should record the rationale for any image scored unacceptable for diagnostic use (scores of 1 or 2). And/or provide comments in image annotation or point to the problem area in the images. Scores should be based on the entire image set, considering all available views, with the exception of the LAVA sequence used for MR-attenuation correction (which should not be considered in the evaluation for image quality).

Secondary Assessments

Site Determination of Diagnostic Acceptability

Based on consensus of at least one radiologist and at least one nuclear medicine physician at the site, diagnostic acceptability of each evaluable image set (including all clinically acquired MR image sets able to be successfully post-processed that are complete image sets [not from cases of withdrawal or critical deviation that could impair to the quality of data]).

Binary diagnostic image quality will be recorded by the site on a single CRF that includes the names and signatures of both the radiologist and nuclear medicine physician making the evaluation, as follows:

"Is the image of acceptable quality for diagnostic use? (Y/N)"

The reader should record the rationale for any "no" answer indicating that the image is not acceptable quality for diagnostic use. And/or provide comments in image annotation or point to the problem area in the images. Scores should be based on all views included in the image set, considering all available views, with the exception of the LAVA sequence used for MR-attenuation correction (which should not be considered in the evaluation for image quality).

Ease of use

Each of the following **ease of use** parameters will be rated by the device operator on a 5-point scale (1 = challenging, 2 = somewhat challenging, 3 = neutral neither challenging nor easy, 4 = somewhat easy, 5 = easy), where scores of ≥ 3 are acceptable, as follows:

- Prescribing and Scanning
 - Prescribing PET scan
 - Prescribing MR scans simultaneous with PET
 - Starting and monitoring scanning
 - Reviewing PET and MR image sets
- General Workflow
 - Overall process of doing this exam
 - Performing exam within acceptable duration to meet normal site workflow requirements

Functionality

Each of the following parameters for **functionality** will be rated by the device operator on a binary (Y/N) scale, as follows:

- Did the system function to view the PET, MR, and/or fused image sets?
- Did the system function to position subject and coils in scanner?
- Did the system function to prescribe and scan this exam? If no, indicate which (PET, MR, and/or fused did not function properly).

If no is indicated for any functionality, the investigator should indicate the reason in a provided area for comments on the Case Report Form (CRF).

Safety Assessments

The description, severity, and device relatedness of any AE or SAE during the study will be recorded. Subjects will, if necessary, be provided with emergency care. In the event of any device issues, the event will be recorded. Safety reporting will be conducted as described in this protocol.

